12.2. Statistical Analysis of Efficacy

Primary and secondary efficacy analyses will be performed on the Per-Protocol population, defined as all randomized subjects who missed no more than 3 treatment visits, completed Visit 10 (primary analysis) and Visit 13 (secondary analysis), and who have not had a major protocol violation over that time period, including the use of a clinically relevant quantity of a prohibited medication as determined by the study Medical Monitor. No missing data imputation will be used for these analyses.

Visit 10 is considered to be the primary efficacy endpoint. In addition, some analyses will also be conducted at earlier and subsequent visits, and treated as exploratory analyses. Some sensitivity efficacy analyses may also be re-performed on the Intent to Treat population, defined as those randomized subjects who have at least one post-baseline visit with required efficacy data collection and who completed Visit 10 with required collection of efficacy data. For those analyses, missing efficacy data for intermediate visits will be imputed using the last observation carried forward (LOCF) procedure. A determination as to the performance of analyses using the Intent to Treat population will be based on the number and pattern of visits missed by randomized subjects. Exploratory analyses using models specified below may also be performed for separate age groups, depending on enrollment outcomes.

For all analyses, two-tail alpha will be set to 0.05 with no adjustment for multiple comparisons. ANOVAs and ANCOVAs will include Site in the model only if doing so improves the sensitivity of the model for comparing treatment groups.

After the last randomized subject has completed Visit 10 the database will be validated, locked through Visit 10 and unblinded for the purpose of analyzing efficacy data through Visit 10. Those analyses are not considered to be interim analyses as the results will be final. Data will continue to be collected through Visit 13 for all subjects, and the full database will subsequently be locked for efficacy analysis (including durability of response) beyond Visit 10, and for the analysis of safety and all other clinical data.

The primary efficacy analysis will be a comparison between treatment groups based on the mean change in Target Wart PWA from Baseline (Visit 2) to Visit 10, using Analysis of Covariance with Baseline PWA as the covariate.

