Page 45 of 53 Amendment 2 Version 3 Date: 05 December 2017 Secondary efficacy analyses will include comparisons between treatment groups based on the following: the proportion of subjects with the Target Wart Clear (PWA = 0) at Visit 10 using Fisher's Exact Test; the proportion of subjects with all treated warts Clear at Visit 10 using a Cochran-Mantel-Haenszel test stratified by number of treated warts; and the mean of per-subject percentages of treated warts that are clear at Visit 10 using Analysis of Variance. The number of treated warts Clear at Visit 10 will also be analyzed using a Cochran-Mantel-Haenszel test stratified by number of treated warts Clear at Visit 10 will also be analyzed using a Cochran-Mantel-Haenszel test stratified by number of treated warts.

Durability of response in the Active treatment group will be evaluated by calculating the proportion of those treated warts achieving a PWA status of Clear at Visit 10 which continue to maintain a PWA status of Clear at Visit 13. This analysis will be performed separately for Target Warts, and for all treated warts. The 95% confidence limits around the calculated proportions will also be calculated in order to estimate the population lower limit value of the observed sample proportions.

Exploratory analyses will be conducted using a subset of the above analysis models, based on the following baseline wart classifications: warts that are determined to be treatment-naive vs. recalcitrant.

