3.1. Number of Subjects and Study Centers

Approximately 120 evaluable subjects will be randomized to one of two treatment arms at approximately 15 investigational centers in the US.

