7.2. General Statistical Considerations

In general, all listings, summaries and analyses will be done and presented by treatment group. Data listings will be produced for all relevant parameters. Summaries of quantitative variables will include the sample size, mean, median, standard deviation, minimum, and maximum. Ordinal variables will be treated as continuous for analysis purposes. For non-ordinal categorical variables, the summaries will include the number and percent of subjects for each outcome. Unless otherwise indicated, for inferential comparisons, statistical significance will be declared if the two-sided p-value is ≤ 0.05 . No alpha adjustments will be made.

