9. STATISTICAL ANALYSIS METHODS

9.1. Statistical Analysis of Efficacy Data

Primary and secondary efficacy analyses will be performed on the Per-Protocol population, defined as all randomized subjects who missed no more than 3 treatment visits, completed Visit 10 (and Visit 13 for purposes of the Visit 13 analysis), and who have not had a major protocol violation over that time period including the use of a clinically relevant quantity of a prohibited medication as determined by the study Medical Monitor. No missing data imputation will be used for these analyses.

Visit 10 is considered to be the primary efficacy endpoint. In addition, some analyses will also be conducted at earlier and subsequent visits, and treated as exploratory analyses. Some sensitivity efficacy analyses may also be re-performed on the Intent to Treat population, defined as those randomized subjects who have at least one post-baseline visit with required efficacy data collection and who completed Visit 10 with required collection of efficacy data. For those analyses, missing efficacy data for intermediate visits may be imputed using the last observation carried forward (LOCF) procedure. A determination as to the performance of such analyses using the Intent to Treat population will be based on the number and pattern of visits missed by randomized subjects. Exploratory analyses using models specified below may also be performed for separate sub-groups, depending on enrollment outcomes.

For all analyses, two-tail alpha will be set to 0.05 unless otherwise specified, with no adjustment for multiple comparisons. ANOVAs and ANCOVAs will include Site in the model only if doing so improves the sensitivity of the model for comparing treatment groups.

After the last randomized subject has completed Visit 10 the efficacy data captured to date in the database will be validated, locked through Visit 10 and unblinded for the purpose of analyzing efficacy data through Visit 10. Those analyses are not considered to be interim analyses as the results will be final. Data will continue to be collected through Visit 13 for all subjects, and the full database will subsequently be locked for efficacy analysis (including durability of response) beyond Visit 10, and for the analysis of safety and all other clinical data.

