The primary efficacy analysis will be a comparison between treatment groups based on the mean change in Target Wart PWA from Baseline (Visit 2) to Visit 10, using Analysis of Covariance with Baseline PWA as the covariate.

Secondary efficacy analyses will include comparisons between treatment groups based on the following: the proportion of subjects with the Target Wart Clear (PWA = 0) at Visit 10 using a one-tail Fisher's Exact Test; the proportion of subjects with the Target Wart Clear or Near-Clear (PWA = 0 or 1) at Visit 10 using a one-tail Fisher's Exact Test; the proportion of subjects with all treated warts Clear at Visit 10 using a Cochran-Mantel-Haenszel test stratified by number of treated warts; the proportion of subjects with all treated warts Clear or Near-Clear at Visit 10 using a Cochran-Mantel-Haenszel test stratified by number of treated warts; the proportion of subjects with all treated warts Clear or Near-Clear at Visit 10 using a Cochran-Mantel-Haenszel test stratified by number of treated warts; the mean of persubject percentages of treated warts that are Clear at Visit 10 using Analysis of Variance; the

mean of per-subject percentages of treated warts that are Clear or Near-Clear at Visit 10 using Analysis of Variance; and the mean of per-subject percent change from baseline PWA for treated warts using Analysis of Variance.

Durability of response in the Active treatment group will be evaluated by calculating the proportion of those treated warts achieving a PWA status of Clear at Visit 10 which continue to maintain a PWA status of Clear at Visit 13. This analysis will be performed separately for Target Warts, and for all treated warts. The 95% confidence limits around the calculated proportions will also be calculated in order to estimate the population lower limit value of the observed sample proportions.

Exploratory analyses may be conducted using a subset of the above analysis models, based on lesion sub-groups including body location, age, time to clearance, and also the following baseline wart classification: warts that are determined to be treatment-naive vs. recalcitrant.

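### The SAP makes both Target Wart responder Fisher tests one-tail, with no level or reason given, while the later-dated protocol sets two-tail 0.05 for all analyses

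*SAP*

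**What the plan says.** SAP 9.1 (dated 21 November 2017) lists two Target Wart responder comparisons and makes each a one-tail Fisher's Exact Test: "Target Wart Clear (PWA = 0) at Visit 10 using a one-tail" and "Target Wart Clear or Near-Clear (PWA = 0 or 1) at Visit 10 using a one-tail". It states no one-tail level and no justification.

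The SAP's general rules are two-sided but leave room for exceptions. Section 9.1 says "For all analyses, two-tail alpha will be set to 0.05 unless otherwise specified, with no adjustment for multiple comparisons". Section 7.2 opens its significance rule with "Unless otherwise indicated, for inferential comparisons, statistical significance will be declared if the two-sided p-value is" and sets the threshold at 0.05.

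Protocol 12.2 (Amendment 2, dated 05 December 2017) has no such room: "For all analyses, two-tail alpha will be set to 0.05 with no adjustment for multiple comparisons". It lists "the proportion of subjects with the Target Wart Clear (PWA = 0) at Visit 10 using Fisher's Exact Test", naming no tail, so its two-tail rule applies. Clear or Near-Clear is not among the protocol's secondary analyses. The SAP synopsis also names Fisher's test for Clear without a tail.

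**The concern.** The SAP and the protocol give different significance rules for the same comparison, and nothing ranks one document over the other. The exception clauses make the one-tail choice permissible within the SAP. They do not amend the protocol, and they do not supply the missing one-tail level.

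The practical risk is a table that counts as a win under one document and not under the other. Target Wart Clear is the first-listed secondary comparison in both. Efficacy data are to be unblinded after the Visit 10 lock, and a choice of rule made after that point would be open to the charge that it was driven by the data.

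**Working it through.** **Inputs from the documents.** "Approximately 120 evaluable subjects will be randomized to one of two treatment arms", allocated 1:1, so 60/60 is the reference split; two-tail alpha 0.05; Fisher's Exact Test.

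**Assumptions.** The one-tail tests use 0.05, because no other alpha appears in either document. The documents give no responder rates, so ranges are used. Arm sizes near 60 are varied because the total is only approximate.

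**Nominal levels.** Two-tail 0.05 allows 0.05 / 2 = 0.025 in the direction favouring A-101 (critical z 1.960). One-tail 0.05 allows the full 0.05 (critical z 1.645), the same as a two-sided test at 2 × 0.05 = 0.10.

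**P-values.** For *a* active responders of *n*, *v* vehicle responders of *m*, and *s* = *a* + *v*:

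P(x) = C(n, x) · C(m, s − x) / C(n + m, s)

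- One-tail p: sum of P(x) over x ≥ a.
- Two-tail p: sum of P(x) over all x with P(x) ≤ P(a).

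Example at 60/60 with 6 vehicle responders: 14 active responders give one-tail p = 0.0423. With equal arms the two-tail value is twice that, 2 × 0.0423 = 0.0846. The two-tail rule is first met at 16 active responders (p = 0.032).

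**Active responders needed, with 3, 6 or 9 vehicle responders.**

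- 60/60: 10, 14, 18 one-tail; 11, 16, 20 two-tail.
- 59/61 (active/vehicle): 10, 14, 17 one-tail; 10, 15, 18 two-tail.

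**Chance of falsely declaring A-101 better, and of a split verdict.** Both are sums over all tables (a, v) of Bin(a; n, p_A) · Bin(v; m, p_V). For a false win, p_A = p_V and the sum covers tables that are significant with active better. For a split verdict, it covers tables significant one-tail but not two-tail.

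| Active/vehicle | False win, two-tail (true rates 10–30%) | False win, one-tail (true rates 10–30%) | Split verdict at 25% v 10% |
|---|---|---|---|
| 60/60 | 1.1–1.5% | 2.8–3.2% | 13.9% |
| 59/61 | 1.8–2.0% | 2.6–3.5% | 8.3% |
| 58/62 | 1.8–2.2% | 2.9–3.3% | 8.8% |

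- Over 70 splits (54–63 per arm, differing by at most 4) and the same null rates, the ratio of one-tail to two-tail false-win rate runs from 1.2 to 2.7, with median 1.7. The one-tail rate does not exceed 3.7%.
- With a wider range of common rates at 60/60, 3% to 50%, the one-tail rate is 0.6–4.1% and the two-tail rate 0.2–1.8%.
- Over five assumed vehicle/active pairs (5/15, 5/20, 10/25, 15/30 and 10/30%) at the three splits, the chance of a split verdict is about 6–15%.

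**The case against.** The best defence is that the SAP is coherent on the tail: it sets a two-sided default, reserves exceptions, and then makes two. The question is directional (active against vehicle), and as far as the plan shows the choice was written before unblinding. One-tail testing is not in itself an error. That stands, but it answers only the SAP's internal consistency. The protocol's rule has no exception, and the level is still missing.

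A second point is that the protocol's later date does not prove that it prevails. That also stands. The dates show that the documents are out of step, not which one governs. Nor is the SAP synopsis evidence of a two-sided intent, since it is silent on the tail.

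Third, the size depends on inference and assumption. If the one-tail tests were meant at 0.025, the false-win rate at 60/60 would equal the two-tail rule's. The five rate pairs lie where borderline tables are common, so 6–15% is not a general figure. Clear or Near-Clear may also have higher rates than those pairs cover. At 60/60 with 20% v 40%, however, power is 71.4% one-tail and 60.0% two-tail. Every favourable two-tail rejection is also a one-tail rejection there, so the split-verdict chance is 71.4 − 60.0 = 11.4%, inside the same range.

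Finally, readers could recompute a two-sided p-value from the counts planned for Tables 14.2.2 and 14.2.3. That limits the harm but does not settle which result the report should call significant.

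**Conclusion.** The concern holds. For both Target Wart responder endpoints the SAP prescribes a one-tail test with no level, and the protocol's rule for all analyses is two-tail 0.05. For Clear, the protocol lists the comparison itself and its two-tail rule covers it. For Clear or Near-Clear, which the protocol does not list, the conflict arises only through that general rule.

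If one-tail means 0.05, the nominal chance of a false win doubles from 0.025 to 0.05, although the exact rates stay below 5%. At plausible assumed rates the two rules would disagree in roughly 6–15% of trials. The consequence is confined to two secondary endpoints in a Phase 2 study with no multiplicity control. The primary ANCOVA and the power statement, which concerns only the primary analysis, are untouched. It should be fixed, and it is not grave.

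**What to change.** Before the Visit 10 lock and unblinding, delete the one-tail wording in both places in SAP 9.1 and specify a two-sided Fisher's Exact Test at alpha 0.05, in line with Protocol 12.2.

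The edit is trivial; the cost is power. Usually one or two more active responders are needed, and none in some unequal splits. For assumed rates of 25% v 10%, power falls from 63% to 49% at 60/60 and from 64% to 55% at 59/61.

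If the sponsor wants a directional test, the alternative is to state one-tail 0.025 with a reason and amend Protocol 12.2 to allow it. At 60/60 this rejects the same tables as the favourable side of the two-tail test; at 59/61 and 58/62 some tables differ. Without the amendment it would still depart from the protocol.

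### The three per-subject all-wart ANOVAs in SAP 9.1 leave out baseline PWA and wart count; pre-specifying them is a cheap precision option, not the repair of an error

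*SAP*

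**What the plan says.** SAP 9.1 sets out the following models.

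- **Primary endpoint** (Target Wart PWA change to Visit 10): analysed "using Analysis of Covariance with Baseline PWA as the covariate".
- **All-treated-warts responder endpoints:** for example "the proportion of subjects with all treated warts Clear at Visit 10 using a Cochran-Mantel-Haenszel test stratified by number of treated warts". The Clear or Near-Clear version is handled in the same way.
- **Per-subject percentage endpoints:** three of them, all by ANOVA. The first counts warts graded Clear: "percentages of treated warts that are Clear at Visit 10 using Analysis of Variance". The second does the same for grades 0 and 1 together. The third is "the mean of per-subject percent change from baseline PWA for treated warts using Analysis of Variance". No covariate, stratum or weight is named for any of them.
- **Extra terms:** "ANOVAs and ANCOVAs will include Site in the model only if doing so improves the sensitivity of the model for comparing treatment groups". No other term is provided for.

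Protocol 12.2 lists only the first of the three: "the mean of per-subject percentages of treated warts that are clear at Visit 10 using Analysis of Variance". The synopses of both documents repeat that one. Neither document explains why the models differ.

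**The concern.** All-treated-warts efficacy is a secondary objective, and the plan measures it in two ways. The responder proportions account for wart count; the per-subject percentages do not. Baseline PWA enters the primary analysis but not the percent-change endpoint built on the same scale.

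There is some reason to expect these factors to matter.

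- Eligible warts have baseline grade 2 or 3 (SAP 5.3), and percent change depends on which.
- Each subject contributes 1 to 4 warts (SAP 5.1).
- Protocol 7.2 describes 1:1 randomization with no stratification by grade or count. With about 60 subjects per arm, some chance imbalance is to be expected.
- The analysis set is Per-Protocol, which is selected after randomization. That adds a modest reason to adjust for measured baseline factors.

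An unadjusted model leaves the effect of any such imbalance in the estimate. Its standard error allows for this, so what may be lost is precision. The values needed for adjustment are already recorded at Visit 2.

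**Working it through.** **1. The plan's own figure.** SAP 7.1 claims more than 90% power for the primary analysis and gives none for these secondary ones. No effect size or SD is stated, so the figure cannot be reproduced. With 60 per arm and two-sided alpha 0.05, 90% power implies a standardized effect of (1.960 + 1.282) × √(2/60) = 0.592.

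**2. How each endpoint depends on the omitted factors.**

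- *Percent change and baseline grade.* A one-grade fall is -1/2 = -50% from grade 2 and -1/3 = -33% from grade 3. Reaching Near-Clear is -50% from grade 2 and -2/3 = -67% from grade 3. Full clearance is -100% from either. Dividing by baseline therefore does not remove the dependence on baseline. This argument applies to percent change only.
- *Percentage Clear and wart count.* Take an illustrative 30% clearance per wart, independent between warts. The chance that all warts clear is 30%, 9%, 2.7% and 0.8% for 1 to 4 warts. The expected percentage Clear is 30% at every count. Its SD is √(0.21/k), or 46, 32, 26 and 23 points for k = 1 to 4. Here wart count alters the spread, not the mean.

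**3. Analytic gain.** Let R² be the share of outcome variance explained by the two factors. Then power = Φ(d√(n/2)/√(1 − R²) − 1.960). With n = 60 and an assumed d = 0.50, the unadjusted case is Φ(2.739 − 1.960) = 78.2%.

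| Assumed R² | 0 | 0.05 | 0.10 | 0.20 | 0.30 |
|---|---|---|---|---|---|
| Power | 78.2% | 80.2% | 82.3% | 86.5% | 90.5% |

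This ignores the degrees of freedom spent, which the simulation counts.

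**4. Simulation.** All inputs are assumptions:

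- 120 subjects, 4000 trials per scenario;
- wart counts 1/2/3/4 in 40/25/20/15% of subjects, and 40% of warts at grade 3;
- vehicle clearance 10%, per-wart odds ratio 4, subject SD 1 on the logit scale;
- adjusted model with mean baseline PWA and wart count as categories, which is four extra parameters;
- log-odds slopes per grade and per extra wart of 0 and 0 (none), -0.7 and -0.3 (moderate), -1.4 and -0.6 (strong).

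Relative efficiency is (SD unadjusted / SD adjusted)².

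| Prognostic strength | Endpoint | SD of estimate, unadj. / adj. | Relative efficiency | Power, unadj. / adj. | Change (points) |
|---|---|---|---|---|---|
| None | % Clear | 6.38 / 6.51 | 0.96 | 89.2 / 87.8 | -1.4 |
| None | % change | 6.23 / 6.35 | 0.96 | 96.8 / 96.4 | -0.4 |
| Moderate | % Clear | 6.54 / 6.50 | 1.01 | 87.5 / 86.8 | -0.7 |
| Moderate | % change | 6.40 / 6.28 | 1.04 | 95.4 / 96.0 | +0.6 |
| Strong | % Clear | 6.81 / 6.54 | 1.08 | 82.4 / 84.7 | +2.3 |
| Strong | % change | 6.65 / 6.17 | 1.16 | 91.3 / 94.1 | +2.8 |

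The Monte Carlo standard error of a single power figure near 87% is √(0.87 × 0.13/4000), about 0.5 points. Under no treatment effect, rejection rates were 0.043 to 0.052 unadjusted and 0.045 to 0.053 adjusted. Mean estimates agreed (20.4 against 20.4 points for % Clear, moderate case). Percentage Clear or Near-Clear was not among the tabulated endpoints.

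**5. Other assumed inputs.** One run used 58 per arm, counts in 50/25/15/10%, and slopes of 0 to -1.5 per grade and 0 to -0.4 per extra wart. It gave relative efficiency 0.99 to 1.05 and gains of 0 to 2.5 points. A further run gave about 0.98 to 1.02 with none to moderate prognostic strength and 1.05 to 1.11 with strong. Its power changes ran from about -1.6 to +4.6 points, which is the widest range seen.

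**6. Break-even.** With four extra parameters and no prognostic value, efficiency was 0.96. Adjustment therefore pays once 0.96/(1 − R²) exceeds 1, that is, at R² above about 0.04.

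**The case against.** The case for leaving the plan alone is substantial, and much of it stands.

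- *Nothing is invalid.* A reader might infer that omitting the factors biases the comparison or inflates type I error. With randomized allocation it does neither, and the simulated rejection rates were nominal.
- *The models differ partly because the endpoints do.* Whether all warts clear depends strongly on how many there are, so stratifying those tests is natural. A per-subject percentage already divides by the count, which largely deals with the mean. A baseline covariate in a change-from-baseline ANCOVA is conventional and does not bind every other endpoint. A reader might infer that the plan regards both factors as prognostic throughout; neither document says so.
- *Adjustment is not free.* In the tabulated runs it lowered power for percentage Clear in two of three scenarios. The sign depends on assumptions that the documents cannot settle.
- *A wart-count covariate does not cure unequal variance.* A percentage based on one wart is noisier than one based on four. Weighting or robust standard errors would address that; a term in the mean model does not.

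What the objection does not remove is the case for fixing baseline terms in advance. It is strongest for percent change, where dependence on baseline is arithmetical. The Site rule leaves no room to add these terms later under the plan as written.

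**Conclusion.** The point holds as a minor, optional improvement. Three secondary endpoints omit two baseline quantities that the same section uses for neighbouring analyses, and no reason is given. The expected effect of adding them is about -1.5 to +4.5 power points. A clear gain appears only if baseline grade or wart count is strongly prognostic, and a loss of one or two points is possible if neither is.

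That range rests wholly on assumed wart-count and grade distributions, effect sizes and prognostic slopes. It supports neither a claim of error nor a claim of certain gain. The case for baseline PWA in the percent-change model is the firmest. The case for wart count rests mainly on consistency with the stratified tests.

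**What to change.** Before the database is unblinded at Visit 10, amend SAP 9.1 so that the three per-subject endpoints are analysed by ANCOVA. The terms would be treatment, the subject's mean baseline (Visit 2) PWA over treated warts, and number of treated warts. Two details should be settled in the text.

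- Include both terms whatever the data show, and not under the conditional rule that applies to Site.
- State how wart count enters. The same categories as the stratified tests give the closest match and cost three degrees of freedom, or four with baseline PWA. A linear term costs one, or two in total.

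If the sponsor prefers ANOVA, a sentence justifying it would also close the point.

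In Protocol 12.2, change only the percentage-Clear endpoint, the one of the three that it lists, and carry that wording into both synopses. No new data are needed. The SAP edit is a matter of wording. The protocol edit is an amendment and falls under the approval rule in Protocol 13.1, so it could be combined with any other amendment under way.
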